4.2. Exclusion Criteria

Subjects who meet any of the following exclusion criteria will not be eligible for enrollment into the study:

Exclusions related to general health:

- Severe extensive colitis as evidenced by:
 - Physician judgement that the subject is likely to require hospitalization for medical care or surgical intervention of any kind for UC (eg, colectomy) within 12 weeks following randomization
 - Current evidence of fulminant colitis, toxic megacolon or recent history (within last 6 months) of toxic megacolon, or bowel perforation
 - Previous total or partial colectomy
- Diagnosis of CD or indeterminate colitis or the presence or history of a fistula consistent with CD.
- Diagnosis of microscopic colitis, ischemic colitis, or infectious colitis.
- Hospitalization for exacerbation of UC requiring intravenous (IV) steroids within 12 weeks of screening (a single dose of IV steroids given is acceptable).
- 5. Positive assay or stool culture for pathogens (ova and parasite examination, bacteria) or positive test for Clostridioides difficile (formerly known as Clostridium difficile) toxin at screening. (Note: If C. difficile is positive, the subject may be treated and retested
 > 4 weeks after completing treatment.)
- Pregnancy, lactation, or a positive serum β-hCG measured during screening.
- 7. Clinically relevant neurological, endocrine, metabolic (including, but not limited to, hypo- and hyperkalemia), psychiatric, cognitive impairment, alcohol/drug abuse/dependence, or other major systemic disease making implementation of the protocol or interpretation of the study difficult or would put the subject at risk.
- Have any of the following conditions or receiving treatments that may affect cardiovascular function:
 - Myocardial infarction, unstable angina, stroke/transient ischemic attack, decompensated heart failure requiring hospitalization or Class III/IV heart failure ≤ 6 months prior to or during the Screening Period

- History or presence of second-degree or third-degree atrioventricular block, sick sinus syndrome, or periods of asystole for > 3 seconds without a functional pacemaker
- History or presence of recurrent symptomatic bradycardia or recurrent cardiogenic syncope
- Screening or Week 0/Day 1 prerandomization vital signs (taken in the sitting position) with a heart rate (HR) < 50 beats per minute (bpm) OR systolic blood pressure (BP) < 90 mm Hg OR diastolic BP < 55 mm Hg. Vital signs may be repeated up to 3 times during a visit to confirm abnormal readings
- Screening or Week 0/Day 1 prerandomization electrocardiogram (ECG) with PR interval > 200 ms or Fridericia's corrected QT interval (QTcF) ≥ 450 ms in men or > 470 ms in women
- Start, stop, change or planned change in dosage of any anti-arrhythmic drugs (Class I to IV) ≤ 1 week before screening or within 1 week before or after randomization
- Forced expiratory volume in 1 second (FEV1) or forced vital capacity (FVC) < 70% of predicted values and FEV1/FVC ratio < 0.70 at screening.
- 10. Uncontrolled diabetes as determined by hemoglobin A1c (HbA1c) > 9% at screening, or subjects with diabetes with significant comorbid conditions such as retinopathy.
- History of macular edema or retinopathy.
- 12. History of active tuberculosis (TB), history of untreated or inadequately treated latent TB infection, active or latent TB infection at screening (refer to Appendix 2 for details on TB screening requirements and interpretation of test results). The following are EXCEPTIONS to this exclusion criterion:
 - Subjects with latent TB, who have been ruled out for active TB, have completed an
 appropriate course of TB prophylaxis treatment per national/local medical guidelines
 or WHO guidelines, have a chest radiograph without changes suggestive of active TB
 infection, and have not had recent close contact with a person with active TB are
 eligible to enroll in the study. It is the responsibility of the Investigator to verify the
 adequacy of previous TB treatment and provide appropriate documentation of
 treatment compliance.
 - Subjects diagnosed with latent TB at screening, ruled out for active TB and received
 at least 4 weeks of an appropriate TB prophylaxis regimen may be rescreened for
 enrollment. Subjects will complete their prophylactic regimen during the trial.
- 13. A clinically significant active infection (eg, serious and/or atypical) ≤ 28 days prior to randomization, required IV medication ≤ 14 days prior to randomization, or that may worsen (in the opinion of the Investigator) if the subject is treated with a drug having immunosuppressant effects (ie, etrasimod). Fungal infection of nail beds is allowed.
- 14. Have human immunodeficiency virus (HIV)/acquired immune deficiency syndrome (AIDS) or test positive for HIV antibodies at screening.
- Have acute or chronic hepatitis B infection or test positive for hepatitis B virus (HBV) at screening (detectable HBV DNA, or positive for hepatitis B surface antigen [HBsAg], or

- negative for HBsAg and positive for anti-hepatitis B core antibody in conjunction with detectable HBV DNA).
- 16. Have current hepatitis C infection or test positive for hepatitis C virus (HCV) at screening as defined by positive for hepatitis C antibody and detectable HCV RNA.
- 17. History of an opportunistic infection (eg, *Pneumocystis jirovecii*, cryptococcal meningitis, progressive multifocal leukoencephalopathy) or history of disseminated herpes simplex or disseminated herpes zoster.
- 18. History of or currently active primary or secondary immunodeficiency.
- 19. History of cancer within the last 5 years, including solid tumors and hematological malignancies (except basal cell and in situ squamous cell carcinomas of the skin that have been excised and resolved) or colonic mucosal dysplasia.
- History of lymphoproliferative disorder, lymphoma, leukemia, myeloproliferative disorder, or multiple myeloma.

Exclusions related to medications:

- Hypersensitivity to etrasimod or any of the excipients or placebo compounds.
- Prior treatment with S1P receptor modulators.
- 23. Treatment with a biologic agent ≤ 8 weeks or a small molecule agent ≤ 5 elimination half-lives and detectable drug level prior to randomization.
- 24. Treatment with an investigational therapy ≤ 3 months prior to randomization.
- Treatment with ≥ 3 biologic agents or ≥ 2 biologics plus a JAK inhibitor approved for treatment of UC.
- 26. Treatment with topical rectal 5-ASA, short-chain fatty acid enemas, or steroids ≤ 2 weeks prior to and during screening.
- 27. Treatment with topical rectal traditional medicine (eg, Chinese medicine), herb enemas, or suppositories ≤ 2 weeks prior to randomization.
- 28. Treatment with methotrexate ≤ 8 weeks prior to and during screening or cyclosporine, tacrolimus, sirolimus, or mycophenolate mofetil (MMF) ≤ 16 weeks prior to and during screening.
- Receipt of a live vaccine ≤ 4 weeks prior to randomization.
- Previous treatment with natalizumab.
- 31. Previous treatment with lymphocyte-depleting therapies (eg, alemtuzumab, anti-CD4, cladribine, rituximab, ocrelizumab, cyclophosphamide, mitoxantrone, total body irradiation, bone marrow transplantation, daclizumab).
- Previous treatment with D-penicillamine, thalidomide, dimethyl fumarate, or pyrimidine synthesis inhibitors.
- Treatment with IV immunoglobulin or plasmapheresis ≤ 3 months prior to randomization.

34. Use of moderate or strong inhibitors or inducers that inhibit or induce at least 2 of the following: cytochrome P450 (CYP) 2C8, CYP2C9, and CYP3A4 (eg, fluconazole, rifampin, enzalutamide) within 4 weeks prior to randomization.

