- 7. Clinically relevant neurological, endocrine, metabolic (including, but not limited to, hypo- and hyperkalemia), psychiatric, cognitive impairment, alcohol/drug abuse/dependence, or other major systemic disease making implementation of the protocol or interpretation of the study difficult or would put the subject at risk.
- Have any of the following conditions or receiving treatments that may affect cardiovascular function:
 - Myocardial infarction, unstable angina, stroke/transient ischemic attack, decompensated heart failure requiring hospitalization or Class III/IV heart failure < 6 months prior to or during the Screening Period

- History or presence of second-degree or third-degree atrioventricular block, sick sinus syndrome, or periods of asystole for > 3 seconds without a functional pacemaker
- History or presence of recurrent symptomatic bradycardia or recurrent cardiogenic syncope
- Screening or Week 0/Day 1 prerandomization vital signs (taken in the sitting position) with a heart rate < 50 beats per minute (bpm) OR systolic blood pressure (BP) < 90 mm Hg OR diastolic BP < 55 mm Hg. Vital signs may be repeated up to 3 times during a visit to confirm abnormal readings
- Screening or Week 0/Day 1 prerandomization electrocardiogram (ECG) with PR interval > 200 ms or Fridericia's corrected QT interval (QTcF) ≥ 450 ms in men or ≥ 470 ms in women
- Start, stop, change, or planned change in dosage of any anti-arrhythmic drugs (Class I to IV) ≤ 1 week before screening or within 1 week before or after randomization
- Forced expiratory volume in 1 second (FEV₁) or forced vital capacity (FVC) < 70% of predicted values and FEV₁/FVC ratio < 0.70 at screening.
- Uncontrolled diabetes as determined by hemoglobin A1c (HbA1c) > 9% at screening, or subjects with diabetes with significant comorbid conditions such as retinopathy.
- 11. History of macular edema or retinopathy.
- 12. History of active tuberculosis (TB), history of untreated or inadequately treated latent TB infection, active or latent TB infection at screening. The following are EXCEPTIONS to this exclusion criterion:
 - Subjects with latent TB, who have been ruled out for active TB, have completed an
 appropriate course of TB prophylaxis treatment per national/local medical guidelines
 or World Health Organization guidelines, have a chest radiograph without changes
 suggestive of active TB infection, and have not had recent close contact with a

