1.3. Benefit/Risk Assessment

Considering the significant unmet need for safe and effective, orally administered treatments for UC, etrasimod may potentially provide therapeutic benefit via S1P receptor modulation.

Adverse events that have been reported with S1P receptor modulators include bradycardia at the first dose or atrioventricular (AV) block, macular edema, hypertension, headache, cough, dyspnea, back pain, influenza, and diarrhea.

Safety and tolerability of etrasimod has been evaluated in Phase 1 studies with healthy adult subjects at single doses up to 5 mg and repeated doses up to 4 mg once daily. Repeated doses of 2 mg have been evaluated in Phase 2 studies of subjects with moderately to severely active UC (refer to the current edition of the IB). Etrasimod was found to be safe and well tolerated in these studies, with no clinically significant safety concerns with respect to vital signs, electrocardiograms (ECGs), pulmonary function tests (PFTs), ophthalmoscopy, or clinical laboratory tests. Etrasimod produced a dose-dependent sustained decrease in total lymphocyte count, which is expected given etrasimod's mechanism of action. Lymphocyte counts were within normal limits by 7 days after the last dose.

Detailed information regarding the known and expected benefits and risks and reasonably expected adverse events of etrasimod can be found in the IB, which serves as a single reference safety document for this study.

Based on the mechanism of action of etrasimod and prior experience with other agents acting via a similar mechanism, monitoring for specific safety parameters are planned for this study, which include auscultation of the lungs as part of the physical exam, PFTs; exclusion of subjects with macular edema or retinopathy, with assessment of optical coherence tomography (OCT) occurring throughout the study, and exclusion of subjects with certain cardiac risks, with assessment of vital signs in the period following dosing.

- Auscultation of lungs will be conducted as part of the physical examination
- Prospective subjects with a history of macular edema or retinopathy will be excluded from the study. All randomized subjects will be assessed by OCT at study entry,

periodically throughout the treatment period, and as clinically indicated any time during the study

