- 10. Adequate hepatic function defined by a total bilirubin level ≤ 1.5 × the upper limit of normal (ULN) range and aspartate aminotransferase (AST) and alanine aminotransferase (ALT) levels ≤ 2.0 × ULN. Subjects with an isolated total bilirubin and normal AST and ALT diagnosed with Gilbert's syndrome may participate.
- 11. Adequate renal function defined by an estimated glomerular filtration rate ≥ 30 mL/min/1.73 m² by the Chronic Kidney Disease Epidemiology Collaboration equation at screening.
- 12. Females must meet either a or b of the following criteria and males must meet criterion c to qualify for the study:
 - a. A female who is not of childbearing potential must meet 1 of the following:
 - Postmenopausal, defined as no menses for 12 months without an alternative medical cause
 - Permanent sterilization procedure, such as hysterectomy, bilateral salpingectomy, or bilateral oophorectomy
 - b. A nonpregnant female of childbearing potential must agree to using a highly effective contraception method during treatment and for 30 days following treatment that can achieve a failure rate of less than 1% per year when used consistently and correctly. The following are considered highly effective birth control methods:
 - Combined (estrogen and progestogen containing) hormonal contraception associated with inhibition of ovulation, which may be oral, intravaginal, or transdermal
 - Progestogen-only hormonal contraception associated with inhibition of ovulation, which may be oral, injected, or implanted
 - Intrauterine device (IUD)
 - Intrauterine hormone-releasing system
 - Bilateral tubal occlusion
 - Vasectomized partner, provided that partner is the sole sexual partner of the female of childbearing potential trial subject and that the vasectomized partner has received medical assessment of the surgical success

- Sexual abstinence (complete sexual abstinence defined as refraining from heterosexual intercourse for the entire period of risk associated with study treatments). The reliability of sexual abstinence needs to be evaluated in relation to the duration of the clinical study and the preferred and usual lifestyle of the subject. Periodic abstinence (calendar, symptothermal, post-ovulation methods) is not acceptable.
- A male subject with a pregnant or nonpregnant female of childbearing potential partner must agree to using condoms during treatment and for 30 days following treatment

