5. REMOVAL OF SUBJECTS FROM STUDY TREATMENT OR ASSESSMENT

5.1. Discontinuation from Study Treatment

A subject's double-blind treatment may be discontinued for any of the following reasons:

- Worsening of disease (Note: If a subject discontinues double-blind treatment at any time starting with the Week 12 assessment, the subject may be eligible to enter the APD334-303 OLE study [Section 5.1.1])
- Adverse event that in the judgement of the Investigator and/or Medical Monitor the subject should not continue study treatment
- Subject noncompliance with the protocol or study treatment that is considered significant by the Medical Monitor
- Investigator decision
- Withdrawal by subject or parent/guardian (if applicable)
- Lack of efficacy
- Lost to follow-up
- Study termination by Sponsor
- Other, non-adverse event

A subject's double-blind treatment must be discontinued for any of the following reasons:

- Decline in PFT values (FEV₁ and/or FVC) below 50% of the predicted values
- Confirmed diagnosis of clinically significant macular edema
- Confirmed diagnosis of active TB
- Subjects who have a cardiovascular treatment-related symptomatic event (eg, chest pain, dizziness, palpitations, lightheadedness, shortness of breath, or syncope) associated with reduction of the heart rate or associated with clinically relevant ECG changes at any time during the 4-hour monitoring period on Day 1 or Day 2 (as applicable) (Section 9.4.2.1)
- Subjects who have not met the discharge criteria on Day 1 after ≥ 4 hours of extended monitoring, or Day 2 by 4 hours post-dose (Table 3).
- Pregnancy (Section 9.9.10)
- Suspected drug induced liver injury as defined by the 2009 FDA Guidance for Industry (FDA 2009)

- ALT or AST > 8 × ULN
- ALT or AST > 5 × ULN for > 2 weeks
- ALT or AST > 3 × ULN and (total bilirubin > 2 × ULN or international normalized ratio > 1.5)
- ALT or AST > 3 × ULN with the appearance of fatigue, nausea, vomiting, right upper quadrant pain or tenderness, fever, rash, and/or eosinophilia (> 5%)

Because transient fluctuations of ALT or AST are common, and progression to severe drug-induced liver injury or acute liver failure is uncommon, automatic discontinuation of study treatment upon finding a greater than 3 × ULN elevation of ALT or AST may be unnecessary. If a drug-induced liver injury is identified, refer to Appendix 6 for guidance.

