9.9.5. Pulmonary Function Test

PFTs will be performed according to the Schedule of Assessments (Appendix 1, Table 6) and includes FEV₁ and FVC measurements. All subjects will have PFTs performed at Screening, Week 12, and Week 52, or at the ET visit. PFTs occurring at the ET visit that are within 4 weeks of the last assessment will only be required if clinically indicated. The 2-Week Follow-Up visit assessment is only required if clinically indicated.

Subjects with a history of mild pulmonary disease (eg, asthma, chronic obstructive pulmonary disease) will have additional PFTs performed at Week 32. Subjects reporting respiratory adverse

events such as dyspnea during the treatment period may return at an unscheduled visit for assessment per Investigator discretion; additional PFTs may be performed as clinically indicated.

When available, DLCO measurements will also be performed. When DLCO is not available, sites should consult the Sponsor or Sponsor's delegate. These tests will be performed at a qualified pulmonary function laboratory or respiratory department. Refer to the American Thoracic Society/European Respiratory Society guidelines for standardization of spirometry and single breath determination of carbon monoxide uptake in the lung (MacIntyre 2005, Miller 2005a, Miller 2005b).

The safety of trial subjects and site staff is paramount, so it is at the Investigator's discretion whether PFT can be safely administered to trial subjects during the treatment period. The Investigator should evaluate on a case-by-case basis how best to proceed based on the subject's medical history, the Investigator's clinical judgement, and in consultation with the Medical Monitor. All reasonable efforts should be made to ensure safety and adherence to the protocol. When available, spirometry may be conducted at the clinical site instead of at the pulmonary laboratory. If the decision is made that it is not appropriate to conduct PFTs due to the safety concerns (eg, SARS-CoV-2 [COVID-19] transmission), then this decision and rationale should be appropriately captured in the subject's source documentation. When available and safe (due to lifting of local restrictions, re-opening of local PFT labs, or improved safety conditions) the tests should be conducted as soon as possible and as close to the timepoints as outlined in the protocol.

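### On its plain reading, exclusion 9 admits FEV1 or FVC already below 50% of predicted when FEV1/FVC is at least 0.70, and for such a measure the mandatory 50% stop does not work as intended

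*Protocol*

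**What the plan says.** **Entry.** Exclusion 9 in Protocol Section 4.2 is "Forced expiratory volume in 1 second (FEV1) or forced vital capacity (FVC) < 70% of predicted values and FEV1/FVC ratio < 0.70 at screening". The synopsis joins the conditions in the same way: "forced vital capacity (FVC) < 70% of predicted values and FEV₁/FVC ratio < 0.70 at screening". No other eligibility criterion puts a number on lung function. Exclusion 7 is a general, judgement-based criterion that reaches "other major systemic disease making implementation of the protocol or interpretation of the study difficult or would put the subject at risk".

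**Stopping.** The mandatory list in Protocol Section 5.1 opens with "Decline in PFT values (FEV₁ and/or FVC) below 50% of the predicted values". It carries no ratio condition and no reference to the participant's own baseline. The separate discretionary list includes "Adverse event that in the judgement of the Investigator and/or Medical Monitor the subject should not continue study treatment", and also Investigator decision.

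**Testing.** Protocol Section 9.9.5 states: "All subjects will have PFTs performed at Screening, Week 12, and Week 52, or at the ET visit". Week 32 is added only for people with known mild lung disease, and further tests may be done when clinically indicated.

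**Why lung function is watched.** Protocol Section 1.3 bases its specific safety monitoring on the drug's mechanism and on experience with similar agents, "which include auscultation of the lungs as part of the physical exam, PFTs" among them.

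**Reporting.** SAP Section 6.3.2.5 flags values below 50% of predicted. The same incidence summary flags falls from baseline of more than 20% and of at least 30%. Change from baseline by visit and a full listing are also planned.

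**The concern.** A stopping threshold is useful when participants start on the safe side of it. Exclusion 9 describes an obstructive pattern, that is, a reduced volume together with a low ratio. Someone whose FEV1 and FVC are reduced in proportion keeps a normal ratio and passes, however low both values are. Such a person can be randomised already beyond the level at which Section 5.1 requires treatment to stop.

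Two things are at stake. One is a mandatory safety rule that, for that participant, either cannot respond to an on-treatment fall in the affected measure or removes them when nothing has changed. The other is consistency between sites, because the text leaves them to choose between those outcomes. The additional Week 32 test for mild lung disease suggests that nothing worse than mild disease was expected at entry, but exclusion 9 does not enforce that when the ratio is preserved.

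**Working it through.** No figure in the plan depends on this point, so there is none to reproduce. The check is of logic, with simple arithmetic.

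**1. Reading exclusion 9.** A single 70% limit governs FEV1 and FVC together, ahead of the *and*. The plain reading is therefore (FEV1 < 70% or FVC < 70%) and ratio < 0.70. If the ratio is 0.70 or more, the criterion is false whatever the volumes.

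**2. Ratio and percent predicted.** Observed ratio = predicted ratio × FEV1% / FVC%. The documents give no predicted ratio, so 0.70 to 0.90 is an assumption. With FEV1% = FVC% = 45, the observed ratio equals the predicted ratio, so the person is not excluded at any predicted ratio of 0.70 or more.

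**3. How low FEV1 must be before exclusion 9 applies, with FVC at 45%.** Limit = 45 × 0.70 / predicted ratio.

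| Assumed predicted ratio | Excluded only if FEV1 is below (% predicted) |
|---|---|
| 0.70 | 45.0 |
| 0.75 | 42.0 |
| 0.80 | 39.4 |
| 0.85 | 37.1 |
| 0.90 | 35.0 |

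**4. Applying the Section 5.1 stop.** Relative fall needed to reach 50% = (entry − 50) / entry. At 70% this is 20/70 = 28.6%; at 51% it is 1/51 = 2.0%. For the 52/48 row, with an assumed predicted ratio of 0.80, the observed ratio is 0.80 × 52/48 = 0.867, so exclusion 9 does not apply. The other rows assume a ratio of at least 0.70.

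| FEV1 / FVC at entry (% predicted) | Stop read as crossing 50% | Stop read as any value below 50% |
|---|---|---|
| 70 / 70 | fires after a fall of more than 28.6% | same |
| 51 / 51 | fires after a fall of more than 2.0% | same |
| 52 / 48 | can fire through FEV1 only | fires at the first on-treatment test, through FVC |
| 45 / 45 | cannot fire | fires at the first on-treatment test |

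The first scheduled on-treatment test is at Week 12.

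**5. Comparison with liver tests.** Protocol Section 4.1 requires AST and "alanine aminotransferase (ALT) levels ≤ 2.0 × ULN". Every numeric ALT/AST stop in Section 5.1 lies above that: more than 3 × ULN with a second finding, more than 5 × ULN for over 2 weeks, and more than 8 × ULN. Nobody meeting the entry limit starts beyond a liver stop. Lung function lacks this ordering.

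**6. The other parsing of exclusion 9.** Suppose it means FEV1 < 70%, or (FVC < 70% and ratio < 0.70). Any FEV1 below 50% is then excluded outright. To enter with FVC below 50%, FEV1 must be at least 70%, which gives an observed ratio above 70/50 = 1.4 times the predicted ratio. That exceeds 1, which is impossible, once the predicted ratio is at least 50/70 = 0.714. On this parsing the gap closes at predicted ratios of 0.714 or more.

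**7. Effect on a reporting row.** One stable participant below 50% would add 1/150 = 0.7 points or 1/75 = 1.3 points to an arm's row, at the planned arm sizes in Protocol Section 10.2. This is the size of one hypothetical case, not evidence that any exists.

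**The case against.** **The stop may still protect.** Section 5.1 can be read as any further on-treatment fall that leaves the value below 50%. A drop from 45% to 40% would then require stopping. This reading is available. It is also true that the rule covers either measure, so a participant with only one value below 50% can still trigger it through the other. A reader might infer that the stop gives no protection to anyone who enters below 50%, and the documents do not support that. What stands is narrower. The wording does not choose between the readings. On the further-fall reading no minimum fall is set, so a trivial one would count.

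**Other safeguards exist.** Screening results must be reviewed before randomisation (Protocol Section 9.3). FEV1 and FVC of 45% could well be judged to fall under exclusion 7. Lung auscultation, a screening chest X-ray, Medical Monitor contact on immediate safety concerns (Section 9.1), extra tests on clinical indication, discretionary stops and Data Monitoring Committee review all remain. They reduce the practical risk considerably. None supplies a numeric entry floor, and most rest on judgement.

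**The SAP row.** A reader might infer that the row for values below 50% would mislead because it has no baseline condition. That goes too far. The same summary reports falls from baseline, and the change table and listing would show that a value was pre-existing. Pairing absolute and change criteria is also how SAP Section 6.3.2.2 treats QTcF.

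**Importance.** The documents do not show that any such participant was enrolled. That is a fair reason to rate the point low.

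**Conclusion.** The point holds as a gap between an entry criterion and a mandatory stop. On its plain reading, exclusion 9 sets no floor on FEV1 or FVC when the ratio is 0.70 or more. For a measure already below 50% of predicted at entry, the Section 5.1 rule cannot fire on that measure if it means crossing 50%. If it means any value below 50%, it ends treatment at the first on-treatment test without any drug-related change. Under the crossing reading it is wholly disabled only when both measures start below 50%.

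The conclusion rests on the plain parsing of exclusion 9; the less natural parsing closes the gap at predicted ratios of 0.714 or more. The number affected is unknown and probably very small. The point does not touch the primary efficacy analysis or the sample size. It is a cheap improvement to safety wording, not a flaw that threatens the trial's conclusions.

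**What to change.** Keep the obstructive criterion and add to exclusion 9, in Protocol Section 4.2 and in the synopsis: *or FEV1 or FVC < 50% of predicted at screening, regardless of the ratio*. Everyone randomised under the new text would then start at or above the stopping level on both measures at screening.

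The cost is one clause and possibly a very few extra screen failures. No new test is needed, because the screening PFT is already done in all subjects. The clause does not create a margin: someone at 51% with a preserved ratio would still enter. It also does nothing for participants already randomised.

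Optionally, SAP Section 6.3.2.5 could count values below 50% as incident only in participants at or above 50% at baseline and show the others separately. This is a presentational preference, since flags relative to baseline are already planned in the same summary. The entry clause stands without it.
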